6.2.1 Efficacy

To evaluate the efficacy of Mydayis, we will explore correlations of TASS ratings with AISRS ratings to examine overall ADHD ratings vs. ADHD ratings throughout the day. We will also explore correlations of changes in neuropsychological assessments of executive function (WebNeuro: Verbal Interference/Stroop, Go/No-Go, CPT/TOVA) versus changes in BRIEF-A measures. Furthermore, will examine potential differential effects of Mydayis in the sample of patients who have defined executive dysfunctions (GEC score on BRIEF-A \geq 65 at placebo-baseline). We will also examine correlations in self- report of ADHD symptoms on the ASRS versus clinician report of ADHD symptoms on the AISRS, and also changes in self-report measures of executive function and emotional dyscontrol on the ASRS versus these measures on the BRIEF-A.

6.2.2 Safety/Pregnancy-related policy

Throughout the study, we will monitor subjects for safety and possible pregnancy. During the screening and eligibility period, we will conduct and report, if applicable clinical laboratory results, to include pregnancy testing, ECG readings and the C-SSRS (conducted as needed per clinician discretion) if there are significant clinical findings. We will monitor subjects weekly for abnormal vital signs, adverse events, and concomitant medications. All adverse events results will be tabulated in manuscripts along with significance testing using the appropriate general linear model.

Subjects will be given a pregnancy contact sheet in the event there is a pregnancy. The pregnant woman will be given a pregnancy inform consent to read and sign to allow us to follow-up with the pregnancy until terminated or full term delivery.

6.2.2.1 Adverse Events Definition and Reporting

Adverse Event

An **adverse event** (AE) is any symptom, sign, illness or experience that develops or worsens in severity during the course of a study. Inter-current illnesses or injuries should be regarded as adverse events. Abnormal results of diagnostic procedures are considered to be adverse events if the abnormality:

- Results in study withdrawal
- Is associated with a serious adverse event
- Is associated with clinical signs or symptoms
- Leads to additional treatment or to further diagnostic tests
- Is considered by the investigator to be of clinical significant

Serious Adverse Event

Adverse events are classified as serious or non-serious. A **serious adverse event (SAE)** is any AE that is:

- Fatal
- Life-threatening
- Requires or prolongs hospital stay
- Results in persistent or significant disability or incapacity
- A congenital anomaly or birth defect
- An important medical event

All adverse events that do not meet any of the criteria for serious should be regarded as **non-serious adverse events**.

Adverse Event Reporting Period

The study period during which adverse events must be reported is normally defined as the period from the initiation of any study procedures to the end of the study treatment follow-up. For this study, the study treatment follow-up is defined as 30 days following the last administration of study treatment.

Preexisting Condition

A preexisting condition is one that is present at the start of the study. A preexisting condition should be recorded as an adverse event if the frequency, intensity, or the character of the condition worsens during the study period.

General Physical Examination Findings

At screening, any clinically significant abnormality should be recorded as a preexisting condition. At the end of the study, any new clinically significant findings/abnormalities that meet the definition of an adverse event must also be recorded and documented as an adverse event.

Post-study Adverse Event

All unresolved adverse events should be followed by the investigator until the events are resolved, the subject is lost to follow-up, or the adverse event is otherwise explained. At the last scheduled visit, the investigator should instruct each subject to report any subsequent event(s) that the subject, or the subject's personal physician, believes might reasonably be related to participation in this study. The investigator should notify the study sponsor of any death or adverse event occurring at any time after a subject has discontinued or terminated study participation that may reasonably be related to this study. The sponsor should also be notified if the investigator should become aware of the development of cancer or of a congenital anomaly in a subsequently conceived offspring of a subject that has participated in this study.

Abnormal Laboratory Values

A clinical laboratory abnormality should be documented as an adverse event if any one of the following conditions is met:

- The laboratory abnormality is not otherwise refuted by a repeat test to confirm the abnormality
- The abnormality suggests a disease and/or organ toxicity

The abnormality is of a degree that requires active management; e.g. change of dose, discontinuation of the drug, more frequent follow-up assessments, further diagnostic investigation, etc.

Hospitalization, Prolonged Hospitalization or Surgery

Any adverse event that results in hospitalization or prolonged hospitalization should be documented and reported as a serious adverse event unless specifically instructed otherwise in this protocol. Any condition responsible for surgery should be documented as an adverse event if the condition meets the criteria for an adverse event.

Reporting of Adverse Events

At each contact with the subject, the investigator must seek information on adverse events by specific questioning and, as appropriate, by examination. Information on all adverse events should be recorded immediately in the source document and in the appropriate adverse event module of the case report form (CRF). All clearly related signs, symptoms, and abnormal diagnostic procedures results should recorded in the source document (though should be grouped under one diagnosis). All adverse events occurring during the study period must be recorded. The clinical course of each event should be followed until resolution, stabilization, or until it has been determined that the study treatment or participation is not the cause. Serious adverse events that are still ongoing at the end of the study period must be followed up to determine the final outcome. Any serious adverse event that occurs after the study period and is considered to be possibly related to the study treatment or study participation should be recorded and reported immediately.

For Narrative Reports of Safety Events

If the report is supplied as a narrative, the minimum necessary information to be provided at the time of the initial report includes:

- Study identifier
- Study Center
- Subject number
- A description of the event
- Date of onset
- Status
- Whether study treatment was discontinued
- The reason why the event is classified as serious
- Investigator assessment of the association between the event and study treatment

Investigator reporting: notifying the study sponsor

The following describes events that must be reported to the study sponsor in an expedited fashion.

Initial Report: within 24 hours:

The following events must be reported to Shire by telephone within 24 hours of awareness of the event:

- Unanticipated problems related to study participation.
- Serious adverse events, regardless of whether they are unexpected.

Additionally, an FDA Form 3500A (MEDWATCH Form) must be completed by the investigator and faxed to the study sponsor, Shire, within 24 hours. The investigator shall maintain a copy of the MEDWATCH Form on file at the study site. Notify:

[name]

Sr. Project Manager, US Medical Clinical Research

On Contractor assignment with Takeda Pharmaceuticals USA, Inc.

Mobile | [contact]

Follow-up report: within 48 hours:

As a follow-up to the initial report, within the 48 hours following the awareness of the event, the investigator shall provide further information, as applicable, on the unanticipated event or the unanticipated problem in the form of a written narrative. This should include a copy of the IRB reporting and any other diagnostic information that will assist the understanding of the event. Significant new information on ongoing unanticipated adverse events shall be provided promptly to the study sponsor.

Adverse Event Reporting Period

The study period during which adverse events must be reported is normally defined as the period from the initiation of any study procedures to the end of the study treatment follow-up. For this study, the study treatment follow-up is defined as 7 days following the last administration of study treatment.

Preexisting Condition

A preexisting condition is one that is present at the start of the study. A preexisting condition should be recorded as an adverse event if the frequency, intensity, or the character of the condition worsens during the study period.

General Physical Examination Findings

At screening, any clinically significant abnormality should be recorded as a preexisting condition. At the end of the study, any new clinically significant findings/abnormalities that meet the definition of an adverse event must also be recorded and documented as an adverse event.

Post-study Adverse Event

All unresolved adverse events should be followed by the investigator until the events are resolved, the subject is lost to follow-up, or the adverse event is otherwise explained. At the last scheduled visit, the investigator should instruct each subject to report any at the last scheduled visit, the investigator should instruct each subject to report any subsequent event(s) that the subject, or the subject's personal physician, believes might reasonably be related to participation in this study.

6.2.3 Pharmacokinetics

Pharmacokinetics will not be conducted for this study.

6.2.4 Biomarkers (if applicable)

Biomarker testing will not be done.

6.3 Study Procedures

Study Flow for Hybrid Study Visits.

During Screening/Baseline Visit (Week -3-0)

The screening visit will be conducted and completed in two parts: remote and in-clinic. During the remote portion, informed consent will be obtained at the screening visit before any study procedures are conducted. Study staff will review the inclusion and exclusion criteria, collect demographics, medical and psychiatric history, prior and concomitant medications, and confirm the ADHD diagnosis via the ACDS v 1.2 and AISRS. Subjects will then be placed on a hold in the screening phase, which can last 28 days up to 90 days. Subjects will be re-consented every 30 days and/or at baseline. Subjects will be called every other week during the holding phase to check willingness to continue to participate. During the dual remote/in-clinic portion, study staff will conduct a physical examination, medical review of systems, vital signs (pulse and blood pressure) and electrocardiogram (ECG/EKG). A blood sample will be collected for routine laboratory testing (hematology and blood chemistry) and a urine sample will be collected for urinalysis, urine pregnancy test (for females of child bearing potential), and urine drug screen. All or some of these clinical examinations can be waived from the screening process if subject can provide record from their primary care doctor and the principal investigator approves them. Trained Study staff will conduct the WebNeuro neuropsychological testing. Participant will complete self-report forms.

During Baseline:

Principal investigator or co-investigator will review all eligibility criteria, inclusive of inclusion and exclusion criteria. Study staff will review any new concomitant medications or adverse events and clinician will conduct a C-SSRS. Eligible participant will be given medication information sheet and bottle of blinded placebo.

1st Dosing information; At the end of Visit -1, eligible participants will begin the singleblind placebo lead-in. Participants will be instructed to take the single-blind placebo the next morning and continue to take IP once daily in the morning and to return all unused capsules at the next study visit. The TASS will be done three times on days of administration. The recommended dosing is at 5 am +/- 1 hour. The first TASS is done at half hour to one-hour post dose (5:30 to 6 am +/- 1 hour), the second TASS is done 4 hours post dose (9am +/- 1 hour) and the third TASS is done 14-15 hours post dose (7pm+/- 1 hour). All TASS administrations will be via telephone.

Placebo Lead-in Phase

Single-Blind Placebo Baseline Lead-in (Week 1, Visit 2)

Eligible participants will return to the study site for the placebo baseline visit within 21-90 days of Visit -1. If unable to come in within the 21 day range, subject will reconsent monthly and have some screening measures redone as per principal investigator discretion. Study staff will review inclusion and exclusion criteria and the results from the ECG, laboratory testing, and urinalysis. The following procedures and assessments will be performed during Visit 1: vital signs, AISRS, Expanded ASRS, CGI-S, and TASS. Concomitant medications and adverse events (AE), if any, will be noted.

At the end of Visit 1, eligible participants will begin the single-blind placebo lead-in. Subjects will be instructed to take the single-blind placebo the next morning, to continue to take IP once daily in the morning and to return all unused capsules at the next study visit. The TASS will be done three times on days of administration. The recommended dosing is at 5 am +/- 1 hour. The first TASS will be done at half hour to one-hour post dose (5:30 to 6 am +/- 1 hour), the second TASS will be done 4 hours post dose (9am +/- 1 hour) and the third TASS will be done 14-15 hours post dose (7pm+/- 1 hour). All TASS administrations will be via telephone.

Single-Blind Placebo Baseline Lead-in (Week 2, Visit 3)

Participants will return to the study site for the second week of Placebo baseline visit within 7 days of Visit 1. The following procedures and assessments will be performed at Visit 2: vital signs, AISRS, CGI-S, WebNeuro battery assessments, TASS, Expanded ASRS, C-SSRS and BRIEF-A. Concomitant medications and AEs, if any, will be noted. Drug accountability and compliance will be performed.

Participants with \geq 30% decrease in total AISRS scores from Visit 1 to Visit 2 will be considered placebo responders and discontinued from the study.

All other participants will be prescribed 12.5mg of Mydayis. They are instructed to take the study medication once daily at 5 am in the morning and to return all unused medication at the next study visit. The TASS will be done three times on days of administration: V1, V3, V4, V5, V6, and V7. The recommended dosing is at 5 am +/- 1 hour. The first TASS will be done at half hour to one-hour post dose (5:30 to 6 am +/- 1 hour), the second TASS will be done 4 hours post dose (9am +/- 1 hour) and the third TASS will be done 14-15 hours post dose(7pm+/- 1 hour). All TASS administrations will be via telephone.

Treatment Phase

MYDAYIS Treatment Phase (Week 1-4, Visit 4-7)

Participants will return to the study site every 7 days during the MYDAYIS treatment phase. The following procedures and assessments may be performed at Visits 4-7: vital signs, AISRS, CGI-S, TASS, Expanded ASRS, C-SSRS, Concomitant medications and AEs, if any, will be noted and drug accountability and compliance will be performed. Note: WebNeuro battery and BRIEF-A assessments are done only at Visit 7.

Participants must take 80% of the prescribed doses of study medication in order to be considered compliant The TASS will be done three times on days of administration. The recommended dosing is at 5 am +/- 1 hour. The first TASS is done at half hour to one-hour post dose (5:30 to 6 am +/- 1 hour), the second TASS is done 4 hours post dose (9am +/- 1 hour) and the third TASS is done 14-15 hours post dose (7pm+/- 1 hour). All TASS administrations will be via telephone.

Subjects will receive a re-supply of study medication at the end of every visit during the Mydayis treatment phase. The dose of Mydayis can be clinically adjusted (in the judgement of the investigator) starting at Visit 4 in 12.5mg increments based upon clinical response and side effects, up to a maximal dose of 37.5 mg/day. Participants will be instructed to return all unused medication at each study visit.

Withdrawal/End of Treatment (Visit 7)

Participants will return to the study site for Visit 7 within 7 days of Visit 6. The following procedures and assessments will be performed at Visit 7: vital signs, AISRS, CGI-S, WebNeuro battery assessments, TASS, Expanded ASRS, C-SSRS and BRIEF-A.

Concomitant medications and AEs, if any, will be noted and drug accountability and compliance will be performed. Participants should report taking at least 80% of the prescribed study medication in order to be considered compliant.

The TASS will be done three times on days of administration. The recommended dosing is at 5 am +/- 1 hour. The first TASS is done at half hour to one hour post dose (5:30 to 6 am +/- 1 hour), the second TASS is done 4 hours post dose (9am +/- 1 hour) and the third TASS is done 14-15 hours post dose (7pm+/- 1 hour).

Participants will be given the Adult ADHD Referral list to help with the transitioning into treatment as usual. Those that complete the study, at the principal investigator's

discretion, as a courtesy can receive a letter stating their diagnosis and participation in the study.

GCP FOLLOWUP: Telephone call

Study staff will make a phone call to the participant within 7 days of Visit 7. Patient will be asked about how they are feeling. Did they transition into treatment as usual? Concomitant medications and AEs, if any, will be noted.

*Unscheduled Visits approved by the principal investigator will be documented in source documents. These visits would be for safety labs/EKGs, early withdrawal or missed visits.

Description	Visit 1		Visit 2	Visit 3	Visit 4	Visit 5	Visit 6	Visit 7	Telephone call
	Week -3-0 Screening	Week -3-0 Screening/ Baseline	Week 1 Placebo Lead in	Week 2 Placebo Lead in	Week 1	Week 2	Week 3	Week 4	1

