4.1 Hypothesis

In subjects with adult ADHD after Mydayis treatment (from end of single-blind placebo lead-in) there will be significant improvement in:

1) Overall symptoms of adult ADHD as measured by the total score on the Adult ADHD Investigator Symptom Rating Scale (AISRS) (primary effect).

2) Overall inattentive (IA) and hyperactive-impulsive (HI) ADHD symptom subsets on the AISRS and overall impairment via the Clinical Global Impression-Severity (CGI-S) scale.

3) Total ADHD symptoms fourteen hours after AM dosing as measured via total scores on the Time Sensitive Adult ADHD Symptom Scale (TASS); Inattentive (IA) and hyperactive-impulsive (HI) ADHD symptom subsets (TASS) subsets.

4) In neuropsychological measurement of Executive Function in the early evening (fourteen to fifteen hours after morning dosing) as measured by (WebNeuro: Verbal Interference/Stroop, Go/No-Go, CPT/TOVA)

5) In clinical symptoms of Executive Function in the early evening, as measured by the BRIEF-A.

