4.3 Secondary Objectives

The secondary objectives of this study are to examine the changes after Mydayis treatment in:

1. Overall inattentive (IA) and hyperactive-impulsive (HI) ADHD symptom subsets on the AISRS and overall impairment via the Clinical Global Impression-Severity (CGI-S) scale.

2. Total ADHD symptoms fourteen to fifteen hours after AM dosing as measured via total scores on the Time Sensitive Adult ADHD Symptom Scale (TASS) and the Inattentive (IA) and hyperactive- impulsive (HI) ADHD symptom TASS subsets.

3. Neuropsychological measurement of executive function in the early evening (fourteen to fifteen hours after morning dosing) as measured by (WebNeuro: Verbal Interference/Stroop, Go/No-Go, CPT/TOVA)

4. Clinical symptoms of executive function, as measured by the BRIEF-A.

5 - Study Design

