6.1.8 Restrictions

Subjects will be screened for drug and alcohol abuse during the prescreen phase. Subjects are instructed on the dangers of drinking alcohol or engaging in drug use during treatment with Mydayis. They will be warned not to use Mydayis for any other condition except the condition for this study: ADHD. Subjects will be instructed and reminded at each study visit not to share this medication with other people, even if they have ADHD. They will be reminded that the Mydayis may harm those for who it is not prescribed for and it is against the law. Subjects will be reminded to report any adverse events or concomitant medications they are taking at each visit.

Subjects will be reminded to take their medication at 5am each morning, as the study assessments are dependent on the consumption of Mydayis at 5:00 am.

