6.4 Statistical Method

6.4.1 Statistical Design

Statistical Analysis Plan: Our primary outcomes are the correlations of TASS ratings with AISRS ratings to examine overall ADHD ratings vs. ADHD ratings throughout the day into early evening. In secondary analyses, we will also analyze the following variables: Evaluation of ADHD symptoms on AISRS; the TASS 1 hour, 4 hours and 14-15 hours post dose: (total, inattentive and hyperactive-impulsive subsets); expanded ASRS (total, inattentive and hyperactive-impulsive, executive function and emotional control subsets); symptoms of executive function (BRIEF-A: GEC, metacognition, behavioral regulation scales and subscales: Inhibit, Shift, Emotional Control, Initiate, Working Memory, Plan/Organize, Organization of Materials, Monitor); and neuropsychological tests (Verbal Interference/Stroop: Color, Word and Interference Score;Go/No-Go: Accuracy, False Negative errors, False Positive errors, and Response Time; CPT/TOVA: Response Time Variability [RVP], Response Time, d', Errors of Omission, Errors of Commission, Post-Commission Response Times, Multiple Responses, Anticipatory Responses).

Our statistical analysis framework will be the general linear regression model. We will choose the distributional family and link function based on the distribution of the outcome variables. Each regression model will predict the outcome as the dependent variable with weeks in trial after the end of the single-blind placebo lead-in as the independent variable.

All analyses will use the ITT sample. For our design, a significant effect of week assesses the significance of the drug effect. We have chosen an IIT analyses as we can include all patients except for placebo responders in the analyses. We have chosen a single-blind placebo lead-in to define placebo responders, which are defined as patients who experience \geq 30% decrease in their total AISRS scores during placebo lead-in treatment and will be discontinued from the protocol. We anticipate that based on the literature that 10% or fewer of patients will be placebo responders and that the overall discontinuation rate in the trial will be 20% (*Manor et al. 2012*). Changes within the day in TASS ratings 1 hour post dose vs. 4 hours post dose vs. 14-15 hours post dose will also be analyzed via the general linear regression model. Correlations between ADHD and executive function ratings will be examined via Spearman's correlation coefficients.

Statistical Power Analysis

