6.4.3 Planned Analyses

6.4.3.1 Primary Analyses

Our statistical analysis framework will be the general linear regression model. We will choose the distributional family and link function based on the distribution of the outcome variables. Each regression model will predict the outcome as the dependent variable with weeks in trial after the end of the single-blind placebo lead-in as the independent variable. All analyses will use the ITT sample. For our design, a significant effect of week assesses the significance of the drug effect. We have chosen an IIT analyses as we can include all patients except for placebo responders in the analyses. We have chosen a single-blind placebo lead-in to define placebo responders, which are defined as patients who experience \geq 30% decrease in their total AISRS scores during placebo lead-in treatment and will be discontinued from the protocol. We anticipate that, based on the literature, 10% or fewer of patients will be placebo responders and that the overall discontinuation rate in the trial will be 20% (*Manor et al. 2012*). The changes within the day in TASS ratings, 1-hour post dose vs. 4 hours post dose vs. 14-15 hours post dose will also be analyzed via the general linear regression model. Correlations between ADHD and executive function ratings will be examined via Spearman's correlation coefficients.

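### Do the post-dose labels and clock windows for the TASS calls conflict enough to need a timing rule?

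*Combined protocol and SAP*

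**What the plan says.** Section 6.3 repeats one TASS paragraph for the placebo lead-in, the treatment phase and the final visit, and Sections 6.3.5 and 6.3.6 repeat it again. On dosing it says "The recommended dosing is at 5 am +/- 1 hour". The three calls follow:

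- first: "The first TASS is done at half hour to one-hour post dose (5:30 to 6 am +/- 1 hour");
- second: 4 hours after the dose, shown as 9 am ± 1 hour;
- third: "the third TASS is done 14-15 hours post dose (7pm+/- 1 hour").

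Section 6.1.8 asks participants to dose at 5 am, "as the study assessments are dependent on the consumption of Mydayis at 5:00 am". Section 6.1.5 says approximately 5 am.

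The evening target varies slightly. Section 4.1 has "Total ADHD symptoms fourteen hours after AM dosing as measured via total scores"; Section 4.3 has "Total ADHD symptoms fourteen to fifteen hours after AM dosing". The analysis sections work with nominal labels: Section 6.4.3.1 compares "1-hour post dose vs. 4 hours post dose vs. 14-15 hours post dose".

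**The concern.** Each call carries two timing instructions, and for the evening call they disagree. A caller working from the clock can phone at 6 pm, which is 13 hours after a 5 am dose and short of the label. A caller working from the dose can phone at 8:30 pm after a 6 am dose, which meets the label but misses the window. The first window opens at 4:30 am, so read by itself it admits a call before a 5 am dose. Section 6.1.8 ties the assessments to a 5:00 am dose, which can be taken to favour the clock; the words about hours after the dose favour the other reading.

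The late-day TASS is a named secondary objective, and the within-day comparison relies on the labels. If the label were often wrong, a result reported for 14 to 15 hours could describe some other time, and the three within-day points could be blurred.

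**Working it through.** **Inputs (Section 6.3).** Dose 5 am ± 1 h = 4 to 6 am. First call: label 0.5 to 1 h, window 4:30 to 7:00 am. Second call: label 4 h, window 8 to 10 am. Third call: label 14 to 15 h, window 6 to 8 pm. Hours after the dose = call time − dose time.

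**Third call, label against window.**

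| Dose | 6–8 pm as hours after dose | 14–15 h as clock time | Both met |
|---|---|---|---|
| 4 am | 14–16 | 6–7 pm | 6–7 pm |
| 5 am | 13–15 | 7–8 pm | 7–8 pm |
| 6 am | 12–14 | 8–9 pm | 8:00 pm only |

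The mismatch is therefore real. The stated 7 pm ± 1 hour does not reproduce 14 to 15 hours.

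**Can both always be met?** For a dose at hour d (24-hour clock), the label gives d + 14 to d + 15 and the window is 18 to 20. They overlap when d + 14 ≤ 20 and d + 15 ≥ 18, that is, for d from 3 to 6. All permitted doses (4 to 6) qualify. The overlap is 1 hour for doses from 4 to 5 am and 6 − d hours after that: 30 minutes at 5:30 am (7:30 to 8:00 pm) and a single instant at 6 am.

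**First and second calls.** The first label gives d + 0.5 to d + 1. Over doses from 4 to 6 am this runs from 4:30 to 7:00 am, exactly the printed window. The second gives d + 4, or 8 to 10 am, again exactly the window. A caller who respects the label never phones before the dose and never leaves the window.

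**Tolerance carried forward.** Suppose each clock time moves with the dose. Then call time = nominal time + (d − 5), and hours after the dose = nominal time − 5:

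- first: 5.5 − 5 = 0.5 h to 6 − 5 = 1 h;
- second: 9 − 5 = 4 h;
- third: 19 − 5 = 14 h.

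All three lie within their labels. The third never reaches the 15-hour end, but it equals the target in Section 4.1.

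**Size of the discrepancy.** The midpoint of the label is 14.5 h and the nominal clock time is 14 h, a difference of 0.5 h. The gap between the second and third calls is 14 − 4 = 10 h, or 14.5 − 4 = 10.5 h. Half an hour is small beside that.

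**The case for a change.** The strongest case for a change is that duration of effect is in the trial's title, that the Introduction and Section 3.2 single out ratings at 14 to 15 hours, and that the text states no order of precedence. Carrying the tolerance forward is an inference, and the document never says it. Section 7.8 describes the calls and direct entry into REDCap without mentioning dose time, so the supplied text does not guarantee that elapsed time can be reconstructed. Writing the rule down would cost little.

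Part of this stands. The two forms are not equivalent, the precedence is implied and not stated, and the fourteen hours of Section 4.1 differs from the fourteen to fifteen of Section 4.3. The rest is weaker:

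- The objectives, hypothesis and analysis sections all give the TASS time points in hours after dosing, and the procedures put the clock time in brackets. A rule that hours after the dose govern would largely restate this.
- The 6 am case is the edge of the tolerance. At the 5 am time given in Section 6.1.8, a call from 7 to 8 pm meets both instructions.
- Pre-dose first ratings, or evening ratings as far out as 12 or 16 hours, require callers to disregard the post-dose instruction. The documents give no distribution of dose or call times from which to estimate how often that would happen.
- Section 7.8 concerns access to source. The case report form and Appendices 13 and 17 were not available, so whether dose and call times are recorded cannot be judged.

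Section 6.4.1 does say "Our primary outcomes are the correlations of TASS ratings with AISRS ratings", which would raise the stakes. Sections 5.1 and 6.4.4, however, make the AISRS total the primary outcome and list the TASS under secondary analyses. That is a separate inconsistency and says nothing about call timing.

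**Conclusion.** No change to the plan follows. This is a drafting slip in a repeated paragraph: the upper end of the evening label was not carried into the clock time. Followed as written, with the call made at the stated hours after the dose and inside the clock window, the schedule works for every permitted dose time, although with no slack at 6 am. Fourteen hours is the lower end of fourteen to fifteen, so a call at 14 hours satisfies both Section 4.1 and Section 4.3.

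The discrepancy is about half an hour between nominal clock time and label midpoint. A caller using only the clock after a 5 am dose would still rate at 13 to 15 hours, within the duration of up to 16 hours that Section 2.1.2 cites from earlier work. The same windows apply in the lead-in and on treatment, so a constant offset would not by itself produce a change across weeks. The AISRS total and the sample size do not depend on these times.

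This rests on two assumptions: that callers heed the hours after dosing, and that calling practice is similar on placebo and on drug. Nothing in the documents suggests otherwise. No effect of extra elapsed-time analyses on any result has been shown, so they would bring no demonstrated gain in a trial of about 32 evaluable patients.
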